7.5.2. Applying Study Medication to the Face

To apply the study medication to Target Lesions on the **FACE** the staff member will follow these treatment instructions:

- Do not apply the study medications to eyes, mouth, mucous membranes, open wounds
- Do not apply the study medication to the eyelids or within 5 mm of the orbital rim
- If, in the investigator's opinion it is needed to ensure no study medication enters the eye:
 - Position the subject in the supine position with the head slightly elevated and angled such that any excess study medication will flow away from the eye.
 - Aclaris Therapeutics will supply sites supplies of white petrolatum (100%) United States Pharmacopeia (USP) that is to be applied along the orbital rim and at the medial and lateral canthi; gently stretch the periorbital skin between the thumb and forefinger at the time of petrolatum application to distend any periorbital rhytides (e.g., "crow's feet") and ensure full coverage of the skin at the base of the rhytides to decrease the likelihood of tracking of the study medication towards the eye
 - Have the subject hold an absorbent pad in the appropriate area of the eye to absorb any excess study medication that might track away from the Target Lesion

- Instruct the subject to keep both eyes closed during the entire study medication treatment procedure
- After the subject is properly prepared and positioned, thoroughly cleanse the Target Lesion by firmly rubbing with a swab/wipe wetted with 70% isopropyl alcohol
- **Subjects randomized to ARM B of cohort 2 will have their DPN lesions medically abraded prior to the application of the A-101 study medication.
- Using firm pressure, while avoiding squeezing the applicator barrel, apply one drop of study medication onto the DPN lesion and then move applicator around in a circular motion to fully saturate the lesion. Using the smaller Q-tip applicator that is supplied massage the A-101 study medication into the DPN lesion for approximately 15 seconds.
- Minimize exposure to the surrounding normal skin
- During the treatment process remove excess study medication from the surrounding skin using a clean absorbent wipe
- Ensure the DPN Target Lesion is wet with study medication at the end of the ~15 second application
- Allow the DPN Target Lesion to remain undisturbed for ~60 seconds
- After ~60 seconds repeat the ~15 second application process
- Repeat the application/waiting cycle until the study medication has been applied to the DPN Target Lesion up to 3 times.

Record the number of times each Target DPN Lesion is treated during a treatment visit and record the time the final treatment is completed for the last treated Target DPN Lesion as the Treatment Completion Time.

It is acceptable to treat multiple Target DPN Lesions at the same time if, in the investigator's opinion, it is practical without exposing non-lesional skin to the study medication.

After completing the study medication treatment to the Target DPN Lesion do not disturb the DPN Target Lesion until just prior to the subject's post-treatment LSR evaluation.

Just prior to the subject's post-treatment LSR evaluation absorb any remaining study medication and gently dab or otherwise dry the Target DPN Lesion with an absorbent pad or dry gauze without wiping or rubbing.

7.5.3. Applying Study Medication to the Neck

To apply the study medication to a Target DPN Lesion on the neck the staff member will follow these treatment instructions:

- Do not apply the study medications to eyes, nose, mouth, mucous membranes, or open wounds
- Position the subject with the plane of the Target DPN Lesion to minimize exposure of the skin surrounding the Target Lesion to the study medication
- Thoroughly cleanse the Target Lesion by firmly rubbing with a swab/wipe wetted with 70% isopropyl alcohol

- **Subjects randomized to ARM B of cohort 2 will have their DPN lesions medically abraded prior to the application of the A-101 study medication.
- Using firm pressure, squeezing in the middle of the applicator, apply one drop of study medication onto the DPN lesion and then move applicator around in a circular motion to fully saturate the lesion. Using the smaller Q-tip applicator that is supplied massage the A-101 study medication into the DPN lesion for approximately 15 seconds.
- Minimize exposure to the surrounding normal skin
- During the treatment process remove excess study medication from the surrounding skin using a clean absorbent wipe
- Ensure the Target DPN Lesion is fully saturated with study medication at the end of the ~15 second application
- Allow the Target DPN Lesion to remain undisturbed for ~60 seconds
- After ~60 seconds repeat the ~15 second application process
- Repeat the application/waiting cycle until the study medication has been applied to the Target DPN Lesion up to 3 times.

7.6. Dose modification

If a subject refuses to allow a study medication initial treatment or retreatment the investigator must report the visit number, visit date, Target Lesion number(s) the subject refused to allow treatment for and the reason for the refusal in the subject's CRF.

If the subject's refusal is associated with an AE, the investigator must also report the event on the appropriate CRF.

The subject must have the Visit 2 initial study medication treatment to all Target Lesions to remain in the study.

The subject does not need to be removed from the study based solely on her/his refusal to have a study medication retreatment at Visit 4.

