5.4. Withdrawal Procedures

If a subject withdraws from the study prior to Visit 8, the reason for and the date of withdrawal from the study must be recorded on the eCRF. If the reason for withdrawal is an adverse event or a clinically significant abnormal laboratory test result, monitoring of the subject will continue until the event has resolved or stabilized, until the patient is referred to the care of a local health care professional, or until a determination of a cause unrelated to the study drug or study procedure is made.

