5.5. Subject Replacement

If a subject is enrolled to the study but does not receive a dose of study drug, then the subject will be replaced.

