12.2. Statistical Analysis of Efficacy Data

Efficacy summaries and analyses (where appropriate) will be based on the per protocol (PP) population of all treated subjects completing all treatment visits and Visit 8 with no major protocol violations. In addition, efficacy summaries may be presented for the intent to treat (ITT) population of all treated subjects with at least one post-baseline visit, using last observation carried forward (LOCF) to impute missing data. Efficacy endpoints will include summary statistics (frequency distributions, proportions, means, medians and standard deviations, as appropriate) by visit for the following parameters: Physician's DPN Lesion Assessment scale results per treated lesion, subject responders defined by Physician's DPN Lesion Assessment scale outcome, and changes from baseline treated lesion diameter.

Comparative inferential analyses will be conducted for data collected from subjects in Cohort 2. The primary efficacy comparisons between the two Cohort 2 treatment groups will be made on the per-subject mean change across all treated lesions in Physician's DPN Lesion Assessment scale from baseline to the final visit using an ANCOVA model. A similar secondary analysis will be performed on the pre-subject mean percent of treated lesions that are clear (PLA=0), and a similar analysis based on clear or near-clear lesions (PLA < 2). Another secondary analysis will be performed on subject responders with all treated lesion PLA scores = 0, as well as a similar analysis on subject responders with all treated lesion PLA scores < 2. An analysis of change from baseline lesion diameter will be conducted using the same methodology as the primary efficacy analysis. All analyses will be conducted at each post-baseline visit where possible. Summaries will also be presented by subject Fitzpatrick Skin Type.

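### A subject treated on some but not all Target Lesions at Visit 2 must leave the study, and so leaves scheduled follow-up, the PP and ITT sets and the ITT-based adverse event summaries

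*Protocol*

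**What the plan says.** Protocol Section 7.6 foresees refusal lesion by lesion: for an initial treatment or a retreatment, the investigator records the visit, the lesion numbers refused and the reason. It then sets a condition for staying in: "The subject must have the Visit 2 initial study medication treatment to all Target Lesions to remain in the study". For retreatment it is more lenient: the subject "does not need to be removed from the study based solely on her/his refusal to have a study medication retreatment at Visit 4". Visit 4 is a treatment visit in Cohort 1 only; Cohort 2 may be retreated at Visits 3 and 5 (Protocol Sections 4 and 7.5).

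Other provisions that bear on a partly treated subject:

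- **Replacement (Protocol 5.5):** "If a subject is enrolled to the study but does not receive a dose of study drug, then the subject will be replaced". A partly treated subject has had a dose, so is not replaced.
- **Follow-up after withdrawal (Protocol 5.4):** "If the reason for withdrawal is an adverse event or a clinically significant abnormal laboratory test result, monitoring of the subject will continue" until it resolves or stabilizes, or another stated end point is reached. Sections 10.2.1 and 10.2.3 likewise follow adverse events. Section 7.6 adds: "If the subject's refusal is associated with an AE, the investigator must also report the event on the appropriate CRF".
- **Schedules (Protocol Tables 2 and 3):** no early-termination visit.
- **Analysis sets (SAP 3.2.1):** PP needs all treatment visits and Visit 8, ITT needs at least one post-baseline visit, and Safety is all treated subjects.
- **Safety summaries:** Protocol 12.4 names the ITT population, although it also says that data from all treated subjects will be presented. SAP 3.7 makes the Safety set the default, but SAP 3.7.3 puts the adverse event overview on ITT.
- **Endpoint and covariate:** the primary comparison "will be made on the per-subject mean change across all treated lesions in Physician's DPN Lesion Assessment scale" (Protocol 12.2). The SAP adds the number of treated lesions as a covariate (3.6.1 and Section 4).

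**The concern.** The rule removes exposed subjects because of something that happens after allocation is known and treatment has begun. Those most likely to meet it are those who tolerated the procedure worst. Safety is part of the primary objective. The graded skin reactions include pigment change, atrophy and scarring, which a Visit 2 assessment cannot show. Protocol Section 2.1 names pigment change and scarring as main drawbacks of existing treatments in this population.

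Only Arm B has lesions abraded before application, so the loss could be unequal between arms. If it were, the randomized comparison and the skin-reaction profile would both rest on subjects selected for tolerance. The ITT repeat of the primary analysis would not help, because LOCF has no post-baseline value to carry forward and the subject is not in that set.

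**Working it through.** The plan states no refusal, dropout or power figure, so there is no figure to reproduce. The check has two parts.

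**1. Follow one subject through the text.** Four Target Lesions, two treated at Visit 2, the other two refused.

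| Question | Result | Source |
|---|---|---|
| Stays in the study? | No | Protocol 7.6 |
| Replaced? | No, a dose was given | Protocol 5.5 |
| Scheduled assessments after Visit 2? | None; 106 − 1 = 105 days unobserved | Protocol Tables 2 and 3 |
| Monitored at all? | Yes, if the withdrawal is for an AE or a clinically significant laboratory result, or an AE is open | Protocol 5.4, 10.2.1, 10.2.3 |
| In PP? | No | SAP 3.2.1 |
| In ITT? | No, no post-baseline visit | SAP 3.2.1 |
| In the Safety set? | Yes, with scheduled data from Visit 2 only | SAP 3.2.1, 3.7 |
| In the AE overview? | No, it uses ITT | SAP 3.7.3 |

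This assumes that removal takes effect at Visit 2 and that no later contact counts as a post-baseline visit.

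**2. Size.** Cohort 2 has 24 subjects randomized 1:2, so Arm A = 24 × 1/3 = 8 and Arm B = 24 × 2/3 = 16. One removal is 1/8 = 12.5% of Arm A or 1/16 = 6.25% of Arm B.

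For an assumed partial-refusal rate p, the chance of at least one removal among n subjects is 1 − (1 − p)^n. With one common rate and n = 24:

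- p = 0%: 0
- p = 2%: 1 − 0.98^24 = 0.38, expected removals 24 × 0.02 = 0.48
- p = 5%: 1 − 0.95^24 = 0.71, expected removals 24 × 0.05 = 1.2

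If the arms differed, say 2% in A and 10% in B (again assumed), the chances are 1 − 0.98^8 = 0.15 and 1 − 0.90^16 = 0.81, with 0.16 and 1.6 expected removals.

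The only related figure in the documents is completion in the six earlier trials (Protocol Table 1):

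- entered: 35 + 172 + 119 + 450 + 487 + 147 = 1410
- completed: 34 + 169 + 116 + 446 + 479 + 139 = 1383
- not completed: 27/1410 = 1.9%, all causes, whole study, no abrasion listed

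Precision is hardly affected. The factor √(1/nA + 1/nB) is 0.433 at 8 and 16, and 0.449 at 8 and 13. The issue is selective loss of data, not power.

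**The case against.** The case for leaving the rule alone has real content, and it shows why several stronger readings fail.

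- **A reader might infer that a removed subject loses all follow-up.** The documents do not support that. Under Protocol 10.1.1, worsening of a Target Lesion assessment is reportable as an AE when study medication is interrupted or discontinued, so stopping because of stinging may well qualify. Monitoring then continues under 5.4 and 10.2.3, and related AEs are followed to a stable outcome under 10.2.1. What is lost is the scheduled, graded assessment. A subject who refuses for discomfort not recorded as an AE has no described follow-up.
- **A reader might infer that removals will concentrate in Arm B and flatter abrasion.** That is plausible but not shown: no tolerability or refusal rate is given for either arm.
- **The event may be rare.** Lesions may be treated at the same time, no minimum number of application cycles is stated, and a subject with one Target Lesion cannot be partly treated. A 5% rate is about 2.6 times the all-cause non-completion of the earlier trials. Those trials do not bound Arm B, but the higher assumed rates are not predictions.
- **A reader might infer that the plan already handles partial treatment.** Averaging over treated lesions makes the endpoint computable. But if refusal depends on arm, the number treated is a post-randomization variable, and adjusting for it can introduce bias.
- **A reader might infer that a Cohort 2 subject who refuses retreatment must leave.** Section 7.6 does not say so. It is silent on Visits 3 and 5, which is a gap and not a removal rule.
- **Retention touches treatment.** A refused lesion entered with PLA of at least 2, so a retained subject would come to the retreatment visits with lesions that meet the PLA criterion in Section 7.5. That interaction is real and the sponsor has to settle it.

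**Conclusion.** The point holds in a limited form. As written, Section 7.6 ends participation for an exposed, partly treated subject. Scheduled assessment to Day 106 stops, and the subject falls outside PP, ITT and the ITT-based adverse event summaries. The Safety set keeps the subject, but with scheduled data from Visit 2 only.

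The number affected is unknown and could be zero. Under assumed common rates of 2% and 5%, the chance of at least one case in Cohort 2 is 38% and 71%. Each case is 12.5% of Arm A or 6.25% of Arm B. A difference between arms is possible because of abrasion, but it is not established. This is worth correcting because the remedy is cheap and the loss, if it occurs, is related to tolerance.

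**What to change.** 1. **Protocol 7.6:** state that any subject with at least one Target Lesion treated at Visit 2 stays in scheduled safety and efficacy assessment through Visit 8, with untreated lesions and the reason recorded.
2. **Protocol 12.4 and SAP 3.7.3:** base all adverse event tables on the Safety set (all treated subjects), in line with SAP 3.7.
3. **SAP 3.6.1:** in the Cohort 2 models, adjust for the number of Target Lesions identified at baseline, not the number treated. State whether a partly treated subject can be PP.
4. **Reconcile** Protocol 7.6 with 7.5 on how refused lesions are handled at later visits, and with the Cohort 2 treatment visits (3 and 5), which the refusal clause does not name. No treatment rule is proposed here; that decision is the sponsor's.

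The cost is an amendment to the wording and two SAP edits, with no new visit types or procedures. The downside is that a few subjects will contribute fewer treated lesions than were selected, so their mean covers only the lesions they accepted for treatment.

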7.7. Previous and Concomitant Therapies

7.7.1. Previous therapies

During Visit 1, the investigator or designee will question the subject to ensure they have not used any excluded therapies.

7.7.2. Concomitant therapies

Concomitant therapies are any new or existing therapy received from Visit 1 until discharge from the study.

Concomitant therapies include drug (*e.g.*, prescription, over-the-counter [OTC]) and non-drug (*e.g.*, chiropractic, physical therapy, energy-based treatments) therapies. Subjects will refrain from receipt of any therapy in compliance with the inclusion/exclusion criteria. Subjects should refrain from changing the use of any concomitant therapies during the study.

All new or modified concomitant therapies used during the study must be recorded in the subject CRF.

7.7.3. Prohibited therapies

During the course of this study, subjects are prohibited from using the following treatment therapies to treat any of the Target Lesions:

- Retinoids (systemic or topical)
- Corticosteroids (systemic or topical)
- Antimetabolites
- LASER, light or other energy-based therapy
- Liquid nitrogen, electrodesiccation, curettage, imiquimod, ingenol mebutate
- Microdermabrasion or superficial chemical peels
- Antibiotics (topical)
- Self-tanner lotions and sprays

The investigator should notify the Medical Monitor immediately if any prohibited therapies are required to ensure subject safety.

Starting with Visit 2, subjects must not apply any topical products (*e.g.*, moisturizers, sunscreens, etc.) to their Target Lesions within **12 hours prior** to any study visit (Note: routine cleansing products are allowed).

After the completion of any study visit where a study medication treatment was performed subjects must **NOT wash/submerge** the Target Lesions for at least **6 hours** and must not apply any topical products to the Target Lesions for at least **6 hours**.

7.8. Wound Care

All subjects will be required to apply Aquaphor to the treated Target DPN Lesions beginning the morning after the application of study medication. Sites will be provided with supplies of Aquaphor that may be dispensed to subjects enrolled to the study. Subjects will be instructed to apply a thin layer of Aquaphor 2x's per day, as needed. Subjects will be instructed to stop applying the Aquaphor 12 hours prior Visit 4 (treatment visit, cohort 1 subjects) or 12 hours prior to Visit 3 and Visit 5 for cohort 2 subjects.

8. ASSESSMENTS OF CLINICAL EFFICACY

8.1. Target Lesion Identification

At Visit 1, the investigator will identify up to 4 Target DPN Lesions located on the subject's body.

At Visit 1, each Target Lesion must:

- Have a clinically typical appearance
- Have a Physician's DPN Lesion Assessment score of ≥ 2
- Have a diameter that is between 2 mm and less than 5 mm
- Have a height or thickness that is ≤ 2 mm
- Be a discrete lesion
- Not be covered with hair which, in the investigator's opinion, would interfere with the study medication treatment or the study evaluations
- Not be in an intertriginous fold
- Not be on the eyelids
- Not be within 5mm of the orbital rim
- Not be pedunculated.
- Not be inflamed, irritated, or excoriated.

Record the approximate location of each Target DPN Lesion on the appropriate body chart in the CRFs. Also, identify the body area (*i.e.*, face, neck) for each Target DPN Lesion in the CRFs. Number the Target DPN Lesions starting with 1 and proceeding up to 4 with no number omitted or reused.

Aclaris Therapeutics will provide the investigational site with standard circular templates to identify the Target DPN Lesions.

8.1.1. Standardized photography

At Visits 1, 2, 3 (prior to retreatment, if applicable for cohort 2 subjects ONLY), 4 (prior to retreatment, if applicable for cohort 1 subjects ONLY), 5 (prior to retreatment, if applicable for cohort 2 subjects ONLY), 6, 7 and 8 qualified investigational center staff member will take standardized color photographs of each Target Lesion.

The photographs are to document the location of the Target DPN Lesion and to assist with relocating the Target DPN Lesion and the Target DPN Lesion ID stickers must be visible in the photographs. The subject's identity will not be revealed in the study photographs.

At Visit 2, the photographs must be taken prior to the study medication treatment. Care must be taken to ensure the same lighting, background, subject positioning relative to the camera and camera settings are used for each photograph.

Sites will be provided with photography equipment and supplies necessary for obtaining the Target Lesion photographs. Detailed instructions for obtaining and managing the photographs will be documented in the study specific Photography Manual and provided to the site at the study initiation visit.

8.1.2. Physician's DPN Lesion Assessment

The Physician's DPN Lesion Assessment is the investigator's assessment of the severity of the Target DPN Lesion at a particular time point. The investigator should NOT refer to any other assessments to assist with these assessments.

At Visits 1, 2, 3 (cohort 2 ONLY), 4 (cohort 1 ONLY), 5 (cohort 2 ONLY), 6, 7 and 8, the investigator will assess the Target DPN Lesion using the scale below and report the one integer that best describes the severity of the Target DPN Lesion. At Visit 2, and if appropriate at Visit 4 for cohort 1 subjects or Visit 3 and Visit 5 for cohort 2 subjects, the investigator must complete the Physician's DPN Lesion Assessment prior to the study medication treatment.

Table 5: Physician's DPN Lesion Assessment Definitions

Physician's DPN Lesion Assessment	
Grade	Descriptor
0	Clear: no visible DPN lesion;
1	Near Clear: a slightly visible DPN lesion; lesion may be macular
2	Small: a visible DPN lesion with a diameter of less than 3 mm
3	Large: a visible DPN lesion that is elevated with a diameter of ≥ 3 mm

At Visit 1 and Visit 2, for the subject to be eligible for enrollment to the study the identified DPN lesions must have a Physician's Lesion Assessment of grade ≥ 2 .

8.1.3. Lesion Dimensions

At Visit 1 and at Visit 2 prior to enrollment the Investigator will be required to measure the diameter and thickness of each Target DPN Lesion. For subjects enrolled to cohort 1 the investigator will measure the diameter of each Target DPN Lesion using the ruler at Visit 4 (prior to retreatment, if applicable), Visit 6, Visit 7 and Visit 8. For subjects randomized to cohort 2, the investigator will measure the diameter of each Target DPN Lesion t Visit 3 (prior to retreatment if applicable), Visit 4, Visit 5 (prior to retreatment if applicable) Visit 6, Visit 7 and Visit 8.

At Visit 1 for the subject to be enrolled and at Visit 2 for the subject to be enrolled each Target DPN Lesion must have:

- A diameter that is between 2 mm and less than 5 mm.
- A height or thickness that is ≤ 2 mm.

